11.2 ENT Examination

ENT examination will be done at Baseline and 60 minutes post dose (or early termination). Findings are expressed as normal, abnormal not clinically significant, and abnormal clinically significant and will be summarized separately for ear, nose, and oropharynx at each time point. A shift table will summarize changes from baseline to 60 minutes post dose.

Confidential Page 17 of 33

11.3 Otoscopy

Otoscopy assessment of TM appearance will be done at Baseline and 60 minutes post dose (or early termination). Findings for contour, color, fluid behind the TM, and translucency will be summarized separately for right and left ear at each time point.

Shift tables will summarize changes from baseline to 60 minutes post dose in normal/abnormal status, with "abnormal" defined as follows:

- Contour: retracted, full, bulging, or perforated
- Color: partly or completely red
- Fluid behind the TM: yes
- Translucency: semi-opaque or opaque

11.4 Vital Signs

Vital signs will be collected at Baseline and at 60 minutes post dose (or early termination). Observed values for oral temperature, respiratory rate, pulse, and systolic and diastolic blood pressure will be summarized at each time point. Changes from baseline will also be summarized for each post baseline time point. Listings will include changes from baseline.

Incidence of clinically meaningful changes from baseline to 60 minutes post dose will be summarized, with clinically meaningful changes defined as follows:

- Systolic BP: $\leq 80 \text{ mmHg or } \geq 140 \text{ mmHg}$
- Diastolic BP: supine $\leq 40 \text{ mmHg or } \geq 90 \text{ mmHg}$
- Pulse rate: ≤ 50 bpm or ≥ 100 bpm
- Respiration rate: < 8 or > 20 breaths per minute

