3.3.1 Inclusion Criteria

Subjects must satisfy all of the following criteria to be included in the study:

- 1. Male and female subjects must be ≥ 18 y of age.
- 2. Subjects must have confirmed AOM diagnosis with moderate to severe bulging of the TM and recent (< 48 hours [h]) onset of ear pain.
- 3. Have moderate to severe ear pain in the affected ear(s), defined as a score of \geq 5 (on a scale of 0-10) on the NRS-11 as evaluated by the subject at Screening.
- 4. Generally good health (other than AOM) as determined by evaluation of medical history and physical examination at Screening.
- 5. Negative urine pregnancy test at Screening for all female subjects of childbearing potential. Results must be available prior to randomisation.
- 6. Able to read and sign written informed consent prior to study participation.

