3.5.2.2 Treatment Procedures (Day 1)

After completion of all screening/baseline procedures, subjects will receive a single intranasal dose (4 sprays per nostril for a total of 8 sprays) of OP0201 20 mg or placebo. Reported AEs will be recorded.

At 10, 20, and 30 min post dose, the following procedures will be performed:

- NRS-11 (both ears will be evaluated regardless if AOM is bilateral or unilateral)
- VAS (both ears will be evaluated regardless if AOM is bilateral or unilateral)

- PGIC
- AEs and concomitant medications

At 60 min post dose, the following procedures will be performed:

- ENT examination (physician investigator to perform otoscopy of the ear, nose, and oropharynx)
- Vital signs (oral temperature, respiratory rate, pulse, and blood pressure measured after at least 3 min of rest in the supine position)
- NRS-11 (both ears will be evaluated regardless if AOM is bilateral or unilateral)
- VAS (both ears will be evaluated regardless if AOM is bilateral or unilateral)
- Otoscopy (physician investigator to evaluate contour, color, fluid, and translucency)
- PGIC
- CGI-I (obtained from the physician investigator who evaluated the subject at baseline and post dose)
- AOM symptoms (tinnitus, dizziness, vertigo, and feeling of fullness or muffled hearing in the ear)
- AEs and concomitant medications
- BI (to be administered separately to the subject and physician investigator after completion of all other assessments)
- Device Experience Questionnaire-Subject
- Device Experience Questionnaire-Study Staff Administering Treatment

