3.5.5 Safety Assessments

Ear, Nose, and Throat Examination: Examination of the ear, nose, and oropharynx will be performed using otoscopy at Screening and at 60 min post dose.

Otoscopy: Otoscopy assessments will be performed by the physician investigator to assess the appearance of the TM in the left and right ear. Measurements will be taken at Baseline and at 60 min post dose. The TM will be rated for the following variables:

- Contour: normal, retracted, full, bulging, or perforated
- Color: normal, partly red, or completely red
- Fluid behind the TM: no/yes; if yes-yellow, translucent, red, blue, or black
- Translucency: translucent, semi-opaque, or opaque

Details of how each variable is to be assessed and categorised are provided in Appendix 8.2.

Vital Signs: Vital signs will be measured at Baseline and at 60 min post dose or Early Termination. Vital signs will include oral temperature (C), respiratory rate (breaths per minute), pulse (beats per minute [bpm]), and systolic and diastolic blood pressure (BP) recorded after at least 3 min of rest in the supine position. Body weight (kg) will also be collected with the vital signs measurements at Baseline only. Repeat measurements may be obtained in the event the initial measurements taken at Baseline are out of range.

Adverse Events: All AEs occurring after the administration of study treatment until the follow-up safety call or early termination will be recorded.

See Section 4, for additional information.

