5.2.7 Safety Analyses

The Safety Analysis Population will be used for all safety analyses by treatment and for all subjects combined (overall) where appropriate. Safety assessments will include AEs, ENT examination, appearance of the TM (otoscopy), and vital signs. Prior and concomitant medications will be summarised using frequencies and percentages of subjects by treatment using the Safety Analysis Population. Only safety assessments with both predose and post-dose data will be analyzed. All other baseline assessments will be listed.

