5.2.7.3 Vital Signs

Vital signs measurements will be summarised using descriptive statistics for all observed timepoints. Additionally, all corresponding changes from Baseline to 60 min post dose will be summarised by treatment.

If appropriate, the incidence of clinically meaningful changes will be summarised at 60 min post dose. Clinically meaningful changes are defined as:

- Systolic BP: $\leq 80 \text{ mmHg or} \geq 140 \text{ mmHg}$
- Diastolic BP: supine $\leq 40 \text{ mmHg or} \geq 90 \text{ mmHg}$
- Pulse rate: ≤ 50 bpm or ≥ 100 bpm
- Respiration rate:< 8 or > 20 breaths per minute

Changes in oral temperature measurements will also be summarised.

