8.6 Study Period and Time Point Definitions

Screening: Day 1 up to dosing.

Baseline Observation: for a given parameter for a given randomized Study Participant, the last observed value before the first dose of study treatment or planned first dose of study treatment if not dosed.

Study Day 1: for a given randomized Study Participant, the day of actual first dose of study treatment or planned first dose of study treatment if not dosed.

Study Day:

- Study day = date of assessment date of dosing + 1, for assessments on or after first dose
- Study day = date of assessment date of dosing, for assessments before first dose

Study Time: time of assessment – time of first dose

Duration:

- Duration in days = end date start date + 1
- Duration in minutes = end time start time

(Nominal Visit) Analysis Time Point: analysis based on data collected at the (nominal visit) time point, where nominal visits are as shown below in Section 8.7.

End of Study (EOS), Study Participant-Level: the date of completion of the last planned study visit or date of discontinuation for any reason.

EOS, Study-Level: the date when all randomized Study Participants have reached Study Participant-Level EOS.

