| 14.3.1.3.3 | TESAEs by PT in Descending Order of Incidence | Safety | | |
| 14.3.1.4 | Non-Treatment-Emergent Adverse Events | Safety | | |

Confidential Page 30 of 33

| 14.3.6 | Concomitant Medications | Safety |
|----------|---|--------|
| 14.3.7.1 | ENT Examination, Observed Values | Safety |
| 14.3.7.2 | ENT Examination, Shifts from Baseline | Safety |
| 14.3.8.1 | Otoscopy, Observed Values | Safety |
| 14.3.8.2 | Otoscopy, Shifts from Baseline | Safety |
| 14.3.9.1 | Vital Signs, Observed Values and Changes from Baseline | Safety |
| 14.3.9.2 | Vital Signs, Incidence of Clinically Meaningful Changes from Baseline | Safety |

Confidential Page 31 of 33

FIGURES

| NUMBER | TITLE | POPULATION |
|-------------|---|------------|
| Exploratory | / Endpoints | |
| 14.2.1.1.1 | VAS Least-Squares Mean (SE) Change from Baseline (PID) | Safety |
| 14.2.1.1.2 | NRS-11 Least-Squares Mean (SE) Change from Baseline (PID) | Safety |
| 14.2.1.2.1 | VAS Least-Squares Mean (SE) SPID | Safety |
| 14.2.1.2.2 | NRS-11 Least-Squares Mean (SE) SPID | Safety |
| 14.2.1.3.1 | VAS Response, 25% | Safety |
| 14.2.1.3.2 | VAS Response, 50% | Safety |
| 14.2.1.3.1 | VAS Response, 75% | Safety |
| 14.2.1.4.1 | NRS-11 Response, 25% | Safety |
| 14.2.1.4.2 | NRS-11 Response, 50% | Safety |
| 14.2.1.4.3 | NRS-11 Response, 75% | Safety |
| 14.2.2.1.1 | PGIC Least-Squares Mean (SE) Change from Baseline | Safety |
| 14.2.2.1.2 | PGIC Response | Safety |
| 14.2.2.2.1 | CGI-I Least-Squares Mean (SE) Change from Baseline | Safety |
| 14.2.2.2.2 | CGI-I Response | Safety |

Confidential Page 32 of 33

LISTINGS

| NUMBER | TITLE | POPULATION | | |
|------------------------|---|--------------------------------|--|--|
| Study Population | | | | |
| 16.2.1 | Study Participant Disposition | Randomized | | |
| 16.2.2.1 | Eligibility and Informed Consent | Randomized | | |
| 16.2.2.2 | Reasons for Screen Failure | Screening excluding Randomized | | |
| 16.2.2.3 | Protocol Deviations | Randomized | | |
| 16.2.3 | Analysis Populations | Randomized | | |
| 16.2.4.1 | Demographic and Baseline Characteristics | Randomized | | |
| 16.2.4.2.1 | Medical History | Randomized | | |
| 16.2.4.2.2 | Prior History Using an Intranasal Device | Randomized | | |
| 16.2.4.3.1 | Physical Examination | Randomized | | |
| 16.2.4.3.2 | Urine Pregnancy Test | Randomized excluding males | | |
| 16.2.4.5 | Prior Medications | Randomized | | |
| 16.2.5 | Study Treatment Exposure | Safety | | |

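### SAP 11.4 and Table 14.3.9.2 promise vital-sign changes from baseline but count them by absolute 60-minute limits, with no baseline condition

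*SAP*

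**What the plan says.** SAP 11.4 first plans summaries of observed vital signs and of their numeric changes. It then adds a second summary: "Incidence of clinically meaningful changes from baseline to 60 minutes post dose will be summarized, with clinically meaningful changes defined as follows". Four criteria follow:

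- systolic pressure at or below 80, or at or above 140 mmHg
- diastolic pressure at or below 40, or at or above 90 mmHg
- pulse at or below 50, or at or above 100 bpm
- respiration below 8 or above 20 breaths per minute

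The table shell in SAP Appendix B, 14.3.9.2, is titled "Vital Signs, Incidence of Clinically Meaningful Changes from Baseline".

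The limits come unchanged from Protocol 5.2.7.3, which says: "If appropriate, the incidence of clinically meaningful changes will be summarised at 60 min post dose". The sentence before that one in the protocol deals with changes from baseline to 60 minutes.

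SAP 8.6 defines baseline as "the last observed value before the first dose of study treatment". On out-of-range readings before dosing, Protocol 3.5.5 says: "Repeat measurements may be obtained in the event the initial measurements taken at Baseline are out of range".

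**The concern.** The label describes a change and the rule describes a state. A subject outside a limit before receiving any study drug meets the criterion at 60 minutes simply by staying there, or by improving without getting back inside the limit. Nothing tells the programmer to exclude such subjects or to show them separately.

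Safety is the primary objective, and among the planned vital-sign tables only this one labels its results clinically meaningful. Its percentages are therefore likely to be quoted. As written, they would mix pre-dose status with post-dose shifts under a title that means only the second.

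**Working it through.** The plan gives no figure to reproduce for this table. The check applies the rule to example readings and then sizes one subject's contribution.

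**1. The rule applied to systolic pressure.** Limits are from SAP 11.4 and the pairs are invented. Three readings of the text are compared: (A) literal, the 60-minute value is outside a limit; (B) the value has changed and is outside a limit at 60 minutes; (C) a new crossing, within limits at baseline and outside at 60 minutes.

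| Baseline to 60 min (mmHg) | Change | A | B | C |
|---|---|---|---|---|
| 160 to 160 | 0 | counted | no | no |
| 150 to 142 | -8 | counted | counted | no |
| 138 to 141 | +3 | counted | counted | counted |
| 150 to 135 | -15 | no | no | no |

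The first two rows show that the choice of reading changes the count. Only A is spelled out, since the definition consists of the limits alone.

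**2. Can out-of-range baselines occur?** Inclusion criterion 4 asks for "Generally good health (other than AOM) as determined by evaluation of medical history and physical examination at Screening", and exclusion criteria 8 and 19 leave other conditions to the investigator's judgment. None sets a numeric vital-sign limit. Protocol 3.5.5 expects out-of-range baseline readings and makes a repeat optional. Such baselines are therefore possible.

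**3. Weight of one subject.** Protocol 5.2.1 plans 12 per arm. One subject out of range at both times adds 1/12 = 8.3 percentage points to the arm under A.

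**4. Illustration of a chance imbalance (assumed counts).** Each arm has 2 new crossings. One arm has no subject who was out of range at baseline and remains so; the other has k.

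- Literal rule, (k + 2)/12: k = 0 gives 2/12 = 16.7%; k = 1 gives 3/12 = 25.0%; k = 2 gives 4/12 = 33.3%.
- New crossings among those in range at baseline, 2/(12 - k): k = 0 gives 2/12 = 16.7%; k = 1 gives 2/11 = 18.2%; k = 2 gives 2/10 = 20.0%.

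With k = 2 in one arm and 0 in the other, the literal table shows a gap of 33.3 - 16.7 = 16.7 points (2/12 before rounding). The new-crossing rate shows 20.0 - 16.7 = 3.3 points, although both arms had the same two events.

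**5. How likely is at least one such subject?** The documents give no prevalence. If a proportion q of subjects is outside a limit at baseline and stays there, the expected number per arm is 12q, and the chance of at least one is 1 - (1 - q)^12.

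- q = 0.10: 1.2 expected; 1 - 0.9^12 = 0.718
- q = 0.20: 2.4 expected; 1 - 0.8^12 = 0.931
- q = 0.30: 3.6 expected; 1 - 0.7^12 = 0.986

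These are results over an assumed range, not estimates for this trial.

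**The case against.** The best reply is that the words incidence and change already imply that something happened after dosing, so a sensible programmer would count only changes that reach a limit. That reading is open, and the text is better called ambiguous than settled. But the condition is nowhere stated, and even a requirement of some change would still count 150 to 142, an improvement.

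A second reply is that subjects are randomised 1:1, so pre-dose abnormality raises both arms equally. This holds in expectation. It does not protect a single table with 12 per arm, where one or two subjects may fall unevenly.

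A third is that true change is reported elsewhere. This stands, and it is the main reason the impact is small. Numeric change is a primary safety endpoint in SAP 4.2.1, is summarised in Table 14.3.9.1 and appears in the listing.

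Some stronger inferences are not supported:

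- A reader might infer that the SAP introduced the baseline reference and failed to log it in section 15. In Protocol 5.2.7.3 the preceding sentence already concerns changes from baseline, so this is not a clear departure. Making an optional summary definite uses an option the protocol gave.
- A reader might fault the rule for passing over large changes within limits. Marking concern by levels is the sponsor's choice, and such changes remain visible in Table 14.3.9.1 and the listing.
- A reader might assume that the table carries no test. SAP 8.3 sets chi-square or Fisher's exact tests as the default for categorical variables unless section 11 says otherwise. Section 11.4 speaks only of summarising, so the position is unclear.

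**Conclusion.** The point holds: label and rule disagree in SAP 11.4 and in the title of Table 14.3.9.2. Read literally, the table can count unchanged or improving subjects as clinically meaningful changes. Each adds 8.3 points to an arm of 12. The total effect cannot be sized, because the documents give no rate of out-of-range baselines; the figures in steps 4 and 5 rest on assumed values.

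The impact is minor. A reader might infer that the primary vital-sign assessment is compromised, but it is not: numeric change is summarised and listed independently of this table, and no decision rule uses the table. What is at risk is a misquoted percentage or an apparent arm difference that reflects pre-dose status, possibly with a p-value attached under the SAP 8.3 default.

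**What to change.** Keep the sponsor's limits, have the sponsor state which count was intended, and make label and rule agree in one of two ways.

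1. **If change was intended:** report a shift from baseline to 60 minutes (below, within or above limits) by treatment, in the style already planned in SAP 11.2 and 11.3. Count newly out of range at 60 minutes among subjects in range at baseline who have a 60-minute value, and show those already out of range at baseline separately.
2. **If status was intended:** retitle Table 14.3.9.2 and reword the lead-in of 11.4 as values outside limits at 60 minutes.

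In either case, add to 11.4 that the table is descriptive only, so that the SAP 8.3 default test does not apply.

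The first option costs one small table and a little programming. The second costs one sentence and one title. Neither needs new data or a new threshold.

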12. EXPLORATORY PARAMETERS

Exploratory parameters will be listed for the Randomized Population and summarized for the Safety Population.

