7. ANALYSIS POPULATIONS

Screening Population: Study Participants who signed an Informed Consent Form and completed any screening procedures.

Randomized Population: Study Participants randomized prior to dosing. Study Participants will be summarized and analyzed per randomization assignment, regardless of treatment actually received.

Safety Population: Study Participants who received at least one spray of study treatment in either nare. Study Participants will be summarized and analyzed per treatment actually received, regardless of randomization assignment.

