- Time to pain relief defined as time point (10, 20, 30, 60 minutes post dose or no pain relief) at which relief was achieved, where "relief" is defined as score < 5 for NRS-11 and at least a 30 mm decrease from baseline for VAS. In the unlikely event that a Study Participant has a baseline VAS less than 30 mm, they will be excluded from the VAS analysis of time to pain relief.
- Response, defined as a 25%, 50%, and 75% reduction in score, at 10, 20, 30, and 60 minutes post dose.

Summaries and Analyses (see Section 13)

• PID_{t_i} will be analyzed using mixed model for repeated measures (MMRM). A summary table will include least-squares (LS) means and standard errors (SEs) for each treatment group and the estimate of treatment group difference with 80, 90, and 95% confidence intervals (CIs) for the difference and associated p-values. LS means and SEs will also be graphically displayed using a line chart. In addition, 80, 90, and 95% CIs and associated p-values for within-group mean changes from baseline will be included in the summary table.

Confidential Page 19 of 33

- SPID_{t_I} will be analyzed using mixed model for repeated measures (MMRM). A summary table will include least-squares (LS) means and standard errors (SEs) for each treatment group and the estimate of treatment group difference with 80, 90, and 95% confidence intervals (CIs) for the difference and associated p-values. LS means and SEs will also be graphically displayed using a line chart. In addition, 80, 90, and 95% CIs and associated p-values for within-group mean changes from baseline will be included in the summary table.
- Response will be analyzed using general estimating equations (GEE). A summary table will include LS means and SEs for each treatment group and the estimate of treatment group difference with 80, 90, and 95% CIs for the difference and associated p-values. Crude response rates will be graphically displayed using a bar chart.
- Percent change from baseline, presence of pain, improvement category, and time to pain relief will be summarized in tables but will not be subjected to statistical inference.

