13.1.4 Missing Observations

One of the assumptions of MMRM is that missing observations are missing at random (MAR), i.e., missingness is unrelated to the variable for which the observation is missing but can be related to another variable on which data have been collected. This assumption is not testable. However, given the short time frame of data collection for exploratory endpoints (60 minutes), it is unlikely that data will be missing not at random (MNAR). It is also unlikely that a substantial proportion (> 10%) of Study Participants will have missing observations. Therefore, the MAR assumption will be considered adequate to address any missing observations for variables analyzed using MMRM.

GEE assumes missing observations are missing completely at random (MCAR); i.e., missingness is independent of all other information whether it was collected or not. Again, due to the short time frame of data collection, this assumption will be considered adequate.

If > 10% of Study Participants have missing observations for a given endpoint, multiple imputation may be used for sensitivity analyses. Under an MNAR model, imputations will be based only on subjects randomized to placebo. The imputation method will be fully conditional specification (FCS) regression with 25 imputations. The imputer's model will include observed values at each time point included in the analysis, including baseline if applicable.

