APPENDIX B: TABLES OF CONTENTS FOR TABLES, FIGURES, AND LISTINGS

TABLES

| NUMBER | TITLE | POPULATION | | |
|------------------|--|--------------------------------|--|--|
| Study Population | | | | |
| 14.1.1 | Study Participant Disposition | Randomized | | |
| 14.1.2 | Eligibility | Randomized | | |
| 14.1.3 | Reasons for Screen Failure | Screening excluding Randomized | | |
| 14.1.4 | Protocol Deviations | Randomized | | |
| 14.1.5 | Analysis Populations | Randomized | | |
| 14.1.6 | Demographic and Baseline Characteristics | Safety | | |
| 14.1.7 | Physical Examination | Randomized | | |
| 14.1.8 | Prior Medications | Randomized | | |
| 14.1.9 | Study Treatment Exposure | Safety | | |
| Explorator | y Endpoints | | | |
| = | VAS Observed Values and Changes from Baseline (PID) | Safety | | |
| 14.2.1.1.2 | NRS-11 Observed Values and Changes from Baseline (PID) | Safety | | |
| 14.2.1.2.1 | SPID, VAS | Safety | | |
| 14.2.1.2.2 | SPID, NRS-11 | Safety | | |
| 14.2.1.3.1 | Presence of Any Pain, VAS | Safety | | |
| 14.2.1.3.2 | Presence of Any Pain, NRS-11 | Safety | | |
| 14.2.1.4.1 | Improvement, VAS | Safety | | |
| 14.2.1.4.2 | Improvement, NRS-11 | Safety | | |
| 14.2.1.5.1 | Time to Pain Relief, VAS | Safety | | |
| 14.2.1.5.2 | Time to Pain Relief, NRS-11 | Safety | | |
| 14.2.1.6.1 | Response, VAS | Safety | | |
| 14.2.1.6.2 | Response, NRS-11 | Safety | | |
| 14.2.2.1.1 | PGIC, Summary Statistics for Observed Values | Safety | | |
| 14.2.2.1.2 | PGIC, Frequency Distributions of Observed Values and Response | Safety | | |
| 14.2.2.2.1 | CGI-I, Summary Statistics for Observed Values | Safety | | |
| 14.2.2.2.2 | CGI-I, Frequency Distributions of Observed Values and Response | Safety | | |
| 14.2.3 | AOM Symptoms | Safety | | |
| 14.2.4 | Blinding Index, Study Participants and Physician Investigators | Safety | | |
| Safety End | points | | | |
| 14.3.1.1 | Summary of TEAE Incidence | Safety | | |
| 14.3.1.2.1 | Incidence of TEAEs by System Organ Class (SOC) and Preferred Term (PT) | Safety | | |
| 14.3.1.2.2 | Incidence of TEAEs Related to Study Treatment by SOC and PT | Safety | | |
| 14.3.1.2.3 | Incidence of TEAEs by SOC, PT, and Maximum Severity | Safety | | |
| 14.3.1.2.4 | TEAEs by PT in Descending Order of Incidence | Safety | | |
| 14.3.1.3.1 | Incidence of TESAEs by SOC and PT | Safety | | |
| 14.3.1.3.2 | Incidence of TESAEs Related to Study Treatment by SOC and PT | Safety | | |

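### The SAP plans no as-randomised efficacy analysis: every efficacy table and figure uses the Safety Population grouped by treatment received

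*SAP*

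**What the plan says.** SAP Section 7 defines two populations with opposite grouping rules. For the Randomized Population: "Study Participants will be summarized and analyzed per randomization assignment, regardless of treatment actually received". The Safety Population is "Study Participants who received at least one spray of study treatment in either nare", and for it: "Study Participants will be summarized and analyzed per treatment actually received, regardless of randomization assignment".

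Section 12 then allocates them for the exploratory parameters, which include all efficacy: "Exploratory parameters will be listed for the Randomized Population and summarized for the Safety Population". The inference sits inside those summaries. Section 12.1.1 specifies that the PID and SPID tables contain "the estimate of treatment group difference with 80, 90, and 95% confidence intervals (CIs) for the difference and associated p-values", and it asks for the same content for response. Section 12.1.2 does so for PGIC and CGI-I.

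Appendix B agrees. Typical entries are "NRS-11 Observed Values and Changes from Baseline (PID) | Safety" and "SPID, VAS | Safety", and no table or figure of an exploratory endpoint carries the Randomized label. Section 13 (Statistical Methods) names no population and plans no as-randomised sensitivity analysis.

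Protocol Section 5.2.2 defines Screening, Randomised and Safety populations, gives no as-treated rule, and assigns none of the three to efficacy. SAP Section 15 does not list the choice among its changes from the protocol.

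**The concern.** Grouping by treatment received is the usual choice for safety. For an efficacy comparison the usual choice is the assigned arm, because that comparison rests directly on the randomisation. Here the as-randomised set is defined, with its own analysis rule, but is not used for any efficacy estimate.

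The plan itself foresees both ways in which the sets can differ. Protocol Section 5.2.3 names administration of the wrong treatment as a possible deviation. SAP Sections 8.6 and 8.7 carry timing rules for randomised participants who were not dosed. Protocol Sections 3.3.3 and 3.5.3 call for early-termination assessments, including NRS-11 and VAS, after any discontinuation between randomisation and 60 minutes. A randomised but undosed subject could therefore have a pain score that no efficacy table counts.

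With 12 per arm, one subject is 1/12 = 8.3% of an arm. Results are called significant from two-sided p < 0.20 (protocol Section 5.2.6.1, SAP Section 8.3), with no multiplicity adjustment (SAP Section 13.1.5). One reassigned or omitted subject could change such a call.

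**Working it through.** **Tracing the population.** Section 12 sends efficacy summaries to Safety. Section 7 makes Safety dosed-only and as-treated. Sections 12.1.1 and 12.1.2 put the tests in those summaries. Appendix B labels the outputs Safety. No step leads to an as-randomised estimate.

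**Inputs.** 12 per arm (protocol Section 5.2.1; 2 × 12 = 24 agrees with the stated total). Two-sided 0.20 level (SAP Section 8.3), critical value 1.282. The documents give no SD, effect size or response rate, so results are in SD units and the subject's distance x is an assumption. The arithmetic uses unadjusted means. A baseline-adjusted MMRM would give somewhat different values.

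**Reference.** SE of the difference = SD × √(2/12) = 0.408 SD.

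**One subject given the wrong kit.** Suppose both arm means equal m and the subject scores m + x. Regrouping leaves arms of 11 and 13. The arm that loses the subject moves to m − x/11 and the arm that gains the subject moves to m + x/13. The difference shifts by x/11 + x/13 = 0.168x.

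| Assumed x | Shift | In SEs | Share of the 0.20 critical value |
|---|---|---|---|
| 1 SD | 0.17 SD | 0.41 | 32% |
| 2 SD | 0.34 SD | 0.82 | 64% |
| 6 NRS points | 6/11 + 6/13 = 0.545 + 0.462 = 1.0 point | needs an SD | needs an SD |

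The 6-point case is an extreme example on a 0 to 10 scale. Dividing 6 by 12 to get 0.5 point would not describe this mechanism, because it changes one value in an arm that keeps its 12 members. Regrouping alters both arms.

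**One undosed subject who has a post-dose score and is left out.** The shift is x/11: 0.09 to 0.18 SD for x of 1 to 2 SD, or 0.22 to 0.45 SE (17% to 35% of the critical value). If the subject has no post-dose score, nothing is lost from the comparison.

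**Response endpoint, assumed 6/12 v 3/12 (25 points).** Moving one responder gives either 7/13 − 2/11 = 0.538 − 0.182 = 36 points, or 5/11 − 4/13 = 0.455 − 0.308 = 15 points.

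**No kit error and nobody undosed.** The populations coincide and every shift is zero.

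**The case against.** The case for leaving the plan alone is substantial. There is one dose, given by study personnel on the day of randomisation (protocol Sections 3.1 and 3.4.6). Kits look identical and are assigned by interactive response technology (protocol Section 3.4.4). There is no second dose, titration or crossover. As-treated analysis is mainly suspect when prognosis or patient choice determines what is received. Here a subject changes group only through an error made blind, and nothing in the documents links such an error to prognosis. As-randomised grouping has its own cost: if 1 of 12 subjects in an arm receives the other product, a true effect is diluted to 11/12 = 92% of its size. Efficacy is exploratory throughout, and the Randomized Population listings and the deviation listing would let a reader find an affected subject. The protocol leaves the analysis set to the SAP (Section 5.2), so there is no contradiction with it.

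All of this stands, and it limits how much the point matters. It does not supply a reason for omitting the as-randomised analysis, which costs almost nothing. The exploratory label also carries limited weight, because the SAP preface intends the planned analyses for regulatory submissions or manuscripts.

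A reader might also infer from Section 13.1.4, where "imputations will be based only on subjects randomized to placebo", that a mis-dosed subject would sit in one arm in the main model and the other in the imputation analysis. The text does not support that. It fixes which subjects inform an optional imputation, and it does not say in which arm the imputed data are then analysed.

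**Conclusion.** The point holds as a gap in the plan: no efficacy estimate, interval or p-value is computed by assigned arm, although the population needed for it is defined. A reader might go further and infer that the pain, PGIC and CGI-I comparisons are biased or have lost their randomised basis. The documents do not support that. Bias would need a kit error or an undosed subject with usable scores, both probably rare here, and the effect is exactly zero if neither occurs.

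If one subject is regrouped, the shift is 0.17 to 0.34 SD, or about 1.0 NRS point in the extreme example. These figures assume equal arm means, 12 per arm, unadjusted means and the stated values of x. They show sensitivity to one subject and do not forecast an error. This is an inexpensive improvement, not a threat to the primary safety objective.

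**What to change.** - In SAP Section 12 and Appendix B, run the efficacy Tables and Figures 14.2.x (PID, SPID, response, PGIC, CGI-I and the descriptive efficacy outputs) on the Randomized Population by assigned treatment.
- State that every randomised subject, including those who discontinue and are replaced, contributes whatever scores were observed. Undosed subjects without post-dose scores are listed only.
- Keep the as-treated Safety Population for the safety tables, exposure and the Blinding Index (Table 14.2.4). Optionally repeat the efficacy models on it as a sensitivity analysis.
- Record the choice in SAP Section 15, before unblinding, so that the analysis set cannot be chosen in response to a known kit error.

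The cost is a short text change and new population labels on the efficacy shells. No new data are needed and the sample size does not change. Baseline characteristics (Table 14.1.6) are planned on the Safety Population, so if the two sets turn out to differ, that table should be repeated for the Randomized Population.
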